## 9.2 SAMPLE SIZE DETERMINATION

## 9.3 POPULATIONS FOR ANALYSES

## 9.4 STATISTICAL ANALYSES

### 9.4.1 GENERAL APPROACH

We will use descriptive statistics to summarize the variables. Analyses will primarily test the hypothesis that intervention participants will have maintenance/reduction of BMI. Secondary analyses will assess whether the intervention leads to improvements in diet and physical activity behaviors and related mediators such as knowledge, attitudes, beliefs, self-efficacy, and social influences. Hypotheses will be tested by comparing changes in outcomes between baseline and follow up. Initial bivariate comparisons will use t tests to compare continuous endpoints and the Wilcoxon matched pairs signed-rank test to compare ordinal endpoints. We will then conduct multivariable analyses (using logistic regression, general linear models, and mixed models) to adjust for potential confounders (such as age, race/ethnicity, gender, SES, and baseline BMI) and to account for the repeated observations per participant. Analyses will include the baseline level of each endpoint as a covariate and a continuous variable for time. Confidence intervals will be constructed around each parameter estimate of the intervention. We will estimate effect sizes for each measure using correction for small sample bias.

To monitor the community-academic partnership, we will track activities such as the communication between community-academic partners, number of participants at CAB meetings, number of manuscripts and presentations by academic-community partners, and policy-related outcomes. We will also ask CAB members to complete annual surveys to gauge how closely the research project aligns with principles of CBPR, including factors they may feel less comfortable discussing in a group, such as level of inclusion and trust.

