**Study Description:**

Specific Aims: 1) Explore strategies for using peer educators and novel mobile health technologies as part of a group lifestyle change program for diabetes prevention among at-risk ethnic minority youth in a New York City community with high disease burden. 2) Refine, implement, and evaluate outcomes for the intervention. Using preliminary data, we will use CBPR to refine our developmentally and culturally appropriate lifestyle intervention for pre-diabetic ethnic minority adolescents. We will then screen at-risk adolescents for pre-diabetes and related lifestyle and biological measures and compare outcomes in adolescents in intervention and wait list control groups to test intervention effectiveness. 3) Further refine the intervention for a larger RCT based on an examination of intervention feasibility, acceptability, and sustainability.

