## 4 STUDY DESIGN

### 4.1 OVERALL DESIGN

We are now testing and evaluating outcomes of our refined intervention to reduce diabetes risk among ethnic minority pre-diabetic adolescents. We will further adapt the program for virtual delivery via a video conferencing platform to enhance access and attendance, and refine the text messaging platform to better support and engage teens.

We will identify at risk for diabetes adolescents and recruit adolescents (BMI in the overweight/obese range and HbA1c 5.7-6.4%) through electronic medical record data queries and referrals from clinical and community sites. Participation will be contingent on adolescent assent/parental consent (ages 13-17) or participant consent (ages 18 years or older). We will randomize pre-diabetic adolescents into intervention and wait list control (delayed intervention) groups to test intervention effectiveness. We will also evaluate the virtual and mHealth components of the intervention through usability testing and data analytics.

The intervention is 12 weekly 90-minute workshops based on feedback from our community advisory board and experts in peer led health education programs. The intervention will be offered via an online platform, Zoom, which is HIPAA compliant. We are testing the effectiveness of a virtual component versus our previous in-person workshop.

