## 9 STATISTICAL CONSIDERATIONS

### 9.1 STATISTICAL HYPOTHESES

**Evaluation of the intervention's impact on the primary study outcome, participants' weights:** We hypothesize that the TEEN HEED intervention will result in maintenance or decrease in BMI percentile. We chose this outcome because weight loss is consistently shown as the most powerful and effective diabetes prevention strategy.

Evaluation of the effectiveness of the TEEN HEED intervention on behaviors and mediators related to weight loss and diabetes prevention: We hypothesize that the intervention will lead to observable changes to diet, physical activity and weight control behaviors and that these and other mediators explain weight loss. We will assess whether the intervention leads to improvements in diet and physical activity behaviors and related mediators such as knowledge, attitudes, beliefs, self-efficacy, and social influences, and improvements in other measures of diabetes risk (such as HbA1c). Hypotheses will be tested by comparing changes in outcomes between baseline and post-intervention follow-up. We will also conduct

exploratory analyses to begin to understand whether any of these factors appear closely linked to pre-diabetes diagnosis or weight loss.

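### Section 9 tests 'maintenance/reduction of BMI' from baseline to follow-up without naming a comparator or defining maintenance, although sections 1.1 and 4.1 promise a wait-list test of effectiveness

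*Combined protocol and SAP*

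**What the plan says.** Section 9.1 gives the primary hypothesis: "We hypothesize that the TEEN HEED intervention will result in maintenance or decrease in BMI percentile". Section 9.4.1 restates it on a different scale: "Analyses will primarily test the hypothesis that intervention participants will have maintenance/reduction of BMI". On the comparison, 9.4.1 says: "Hypotheses will be tested by comparing changes in outcomes between baseline and follow up". Section 9.1 has a near-identical sentence.

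On method, 9.4.1 says: "Initial bivariate comparisons will use t tests to compare continuous endpoints and the Wilcoxon matched pairs signed-rank test to compare ordinal endpoints". It does not say whether the t tests are paired or two-sample. It then plans multivariable models that adjust for potential confounders, take the baseline value as a covariate and include time. It adds: "Confidence intervals will be constructed around each parameter estimate of the intervention". No null value, tolerated increase, significance level or success rule appears in section 9, and neither a wait list nor a control group is mentioned there. Headings 9.2, 9.3 and 9.4.2 carry no text.

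The design sections say more:

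- The Study Description in 1.1 will "compare outcomes in adolescents in intervention and wait list control groups to test intervention effectiveness".
- Section 4.1: "We will randomize pre-diabetic adolescents into intervention and wait list control (delayed intervention) groups to test intervention effectiveness". Section 5.5 also says that eligible adolescents will be randomised to these two groups.
- Section 6.1.1 refers to wait-list control participants when describing consent for text messaging.
- Section 6.3 says that participants in this pilot are not randomised.
- Section 4.1 adds another comparison: "We are testing the effectiveness of a virtual component versus our previous in-person workshop".

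The scale is BMI percentile in 1.1, 8.1 and 9.1, but BMI in sections 3 and 9.4.1. Follow-up is at 3 months in 1.3 and 4.4, but at 5 and 12 months in the site description in 1.1.

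**The concern.** A claim of maintenance or reduction has two parts that need different evidence. A test of mean change against zero can support a decrease. It cannot support maintenance by failing to reject, because failure to reject is also what a small study produces when BMI has risen. With no limit or rule fixed in advance, what counts as maintenance could be settled after the data are seen.

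The larger issue is attribution. The documents say the study will test effectiveness. A baseline-to-follow-up change in one group mixes any programme effect with growth, secular change and other influences. Regression to the mean may also contribute by an unknown amount, reduced where the baseline visit is a fresh measurement after record-based selection. Only a concurrent comparison separates these, and section 9 does not say that one will be made. An analyst following section 9 could report a pre-post contrast under a heading of effectiveness.

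**Working it through.** **Side-by-side reading.** The plan has no sample size, power or significance level to reproduce, so the first check is textual.

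| Question | Section 9 | Elsewhere |
|---|---|---|
| Comparator | none named | wait list (1.1, 4.1, 5.5, 6.1.1); previous in-person workshop (4.1) |
| Randomised? | not stated | yes (4.1, 5.5); no (6.3) |
| Scale | BMI percentile (9.1); BMI (9.4.1) | BMI percentile (1.1, 8.1); BMI (3) |
| Time point | post-intervention or follow-up, undated | 3 months (1.3, 4.4); 5 and 12 months (1.1) |
| Rule for maintenance | none | none |

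The matched-pairs Wilcoxon test points to within-person comparisons. The baseline covariate, the confounder adjustment and the reference to an intervention parameter could fit an arm comparison. Neither reading is settled by the text.

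**Illustration of why the rule matters.** Assumptions not in the documents: two-sided 5% paired t test, and changes expressed in SDs of the change. For n, section 2.2 gives 41 intervention participants and 73% retention in the earlier in-person cohort: 41 × 0.73 = 29.9, so n = 30. This treats overall retention as equal by arm.

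- Noncentrality for a true gain of 0.3 SD: 0.3 × √30 = 1.643. Critical value: t(0.975, 29) = 2.045.
- P(non-significant) = P(−2.045 < T < 2.045), T noncentral t with 29 df = 0.645. At an arbitrary smaller n = 20 it is 0.753.
- 95% CI half-width: 2.045/√30 = 0.373 SD. An observed mean change of exactly zero would still leave a gain of 0.37 SD inside the interval.
- If maintenance instead required an observed mean at or below zero: Φ(−1.643) = 0.050.

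The same true gain would therefore be called maintenance in 64% or 5% of trials, depending on a rule the plan does not state.

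**What each remedy can detect.**

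- Between arms, 30 versus 36 completers (49 × 0.73 = 35.8), one baseline covariate, df = 30 + 36 − 3 = 63. The standard error is √(1/30 + 1/36) = 0.247 residual SD, and 80% power needs a true difference of 0.70 residual SD.
- Single arm, true change zero, n = 30. The chance that the upper 95% limit falls below 0.3 SD is 36%, and 80% needs 90 completers. With a 0.5 SD limit the chance is 75%, and 80% needs 34.

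**Clustering by workshop group.** Section 2.2 gives 10-15 teens per group. The 41 allocated form 41/15 = 2.7 to 41/10 = 4.1, so about 3-4 groups. Those analysed per group are 10 × 0.73 = 7.3 to 15 × 0.73 = 10.95. For an assumed ICC of 0.01-0.05, the design effect 1 + (m − 1) × ICC runs from 1 + 6.3 × 0.01 = 1.063 to 1 + 9.95 × 0.05 = 1.498.

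- Single arm: the SE rises by √1.063 − 1 = 3% to √1.498 − 1 = 22%.
- 30 versus 36, with only the intervention arm clustered: √[(DE/30 + 1/36)/(1/30 + 1/36)] − 1 = 2% to 13%.

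**The case against.** The best defence is that 9.4.1 does contain the pieces of an arm comparison. The t tests belong to initial bivariate work. The later models adjust for confounders and baseline, and interval estimates are promised for the intervention parameter, which makes most sense with a comparison group. This stands as far as it goes. A reader might infer that section 9 commits the trial to a paired pre-post test, or has dropped the wait list. The documents do not support either inference. They show only that the contrast is unnamed. It also follows that baseline adjustment and confidence intervals are already planned and need not be added.

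A second defence is that this is a pilot leading to a larger trial, and that section 9 may simply follow 6.3. The pilot status does weaken the call for a formal maintenance margin, since estimation with a CI serves a pilot better. It does not rescue the effectiveness claim, which 1.1 and 4.1 make in terms.

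Third, the magnitude is wholly assumed. That is correct. The figures show sensitivity to an unstated rule, and reading 64% as this trial's error rate would be wrong.

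Finally, one might say that 1.1 contradicts 6.3 on randomisation. It does not: the Study Description plans a wait-list comparison without saying how groups are formed. The contradiction is between 4.1 and 5.5 on one side and 6.3 on the other.

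**Conclusion.** The point holds in this form. Section 9 states its primary test as maintenance or reduction of BMI judged against baseline, names no comparator and defines no group term, while 1.1 and 4.1 promise a wait-list test of effectiveness and the design sections disagree on randomisation. If the analysis is run pre-post, it cannot support an effectiveness conclusion, and a non-significant change is not evidence of maintenance. The importance rests on that unsupported conclusion and not on the missing margin alone.

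The size for this trial cannot be computed, because N, SD, significance level and margin are not given. Under the stated assumptions, a true 0.3 SD gain is missed in 64% of trials at n = 30. Regression to the mean is not quantified, and clustering is a secondary matter.

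**What to change.** Reconcile 4.1 and 5.5 with 6.3, and align 1.1 and 6.1.1 with the outcome. Name one primary scale (BMI or BMI percentile) and one primary time point (3 months, or 5 or 12 months). Then write one of the following under 9.4.2.

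1. **A wait-list arm is run.** The primary analysis is the between-arm difference in the follow-up BMI measure, using the baseline adjustment already planned in 9.4.1, with its 95% CI. Any effectiveness claim rests on that contrast, and within-arm change is descriptive. If allocation is not randomised, adjust also for the confounders listed in 9.4.1 and label the result non-randomised.
2. **There is no control arm.** Report mean change with its 95% CI, make no effectiveness claim, and state that non-significance will not be read as maintenance. A formal maintenance limit is optional in a pilot. If one is used, fix it in advance and require the upper confidence limit to lie below it.

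In either case, treat any comparison with the earlier in-person cohort as descriptive, and say how clustering by workshop group is handled. Three or four groups are too few to estimate an ICC, so show the interval under an assumed range.

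The cost is mainly wording. Section 1.3 already schedules height and weight at baseline and 3 months; a wait-list arm needs the same follow-up measurement before its own workshops begin. The downside is that the pilot may be inconclusive, as the detectable differences above show.

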## 5.5 STRATEGIES FOR RECRUITMENT AND RETENTION

The Principal Investigator [name], Research Coordinator [name] and community partners working on this study previously identified venues for recruitment of adolescents in East

and Central Harlem including youth community based organizations, after school programs, and health care centers.

Recruitment sites may include the following community organizations in East Harlem with whom we have previously collaborated: Union Settlement Association, Harlem RBI, East Harlem Boys Club, Children's Aid Society, Stanley Isaacs Neighborhood Center, SCAN(SUPPORTIVE CHILDREN'S ADVOCACY NETWORK), Harlem Children's Zone, and other interested organizations to be identified by our community partners and project board. Possible clinical sites for recruitment include Mount Sinai's Adolescent Health Center, Mount Sinai's pediatric endocrine clinic, Mount Sinai's Pediatrics Associates practice, Settlement Health, Boriken Neighborhood Health Center, the Institute for Family Health, Mount Sinai School Based Health Clinics, and Mount Sinai Pediatric Emergency Rooms.

We will obtain provider referrals from community based clinics. We will use Mount Sinai's Data Warehouse and/or EPICs slicer/dicer to identify potentially eligible subjects for recruitment from the Mount Sinai General Pediatric Faculty Practice, Pediatric Endocrinology and Diabetes Center, and the School Based Health Clinics. We will request the following fields:

Name, medical record number, date of birth/age, address, gender, parent or guardian name, contact information for teens 18-19 (including telephone number or other numbers provided), parent or guardian contact information for teens ages 13-17 (including telephone number or other numbers provided), BMI (BMI percentile when available), medications prescribed, and laboratory values from the past year: Glucose/preserved glucose, hemoglobin A1c (values), total insulin (values), and lipid panels (values). We will request information for eligible patients whose medical records contain the following diagnoses codes: overweight, obesity, prediabetes, insulin resistance, and acquired acanthosis nigricans.

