#### 6.3 MEASURES TO MINIMIZE BIAS: RANDOMIZATION AND BLINDING

We are not randomizing participants for this pilot study.

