#### 9.4.8 TABULATION OF INDIVIDUAL PARTICIPANT DATA

- We aim to Recruit and enroll adolescents from clinical and community sites starting in the Spring 2021. Provisions may be made depending on the novel coronavirus pandemic.

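### The covariates listed in 9.4.1 cannot adjust its before-after change for confounding; only a concurrent wait-list contrast could separate the intervention from shared drift in BMI

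*Combined protocol and SAP*

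**What the plan says.** Section 9.4.1 gives the primary aim: "Analyses will primarily test the hypothesis that intervention participants will have maintenance/reduction of BMI". It gives the test as "Hypotheses will be tested by comparing changes in outcomes between baseline and follow up", with a matched-pairs signed-rank test for ordinal endpoints, which is a within-person comparison. It then plans three kinds of multivariable model (logistic, general linear and mixed), whose stated purpose is "to adjust for potential confounders (such as age, race/ethnicity, gender, SES, and baseline BMI) and to account for the repeated observations per participant". Two more terms follow: the baseline level of the endpoint, and continuous time. Intervals are promised for the intervention's parameters, but no arm or arm-by-time term is written.

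Four other places bear on this:

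- **Allocation.** Section 6.3 says "We are not randomizing participants for this pilot study". Sections 4.1 and 5.5 say teens will be randomised to intervention or wait list.
- **Visits.** The schedule (1.3) and 4.4 give a baseline visit and one 3-month follow-up, with demographics at baseline only. The synopsis mentions 5 and 12 months; I follow the schedule.
- **Outcome.** Section 9.1 says "We hypothesize that the TEEN HEED intervention will result in maintenance or decrease in BMI percentile", whereas 9.4.1 says BMI.
- **Calendar.** Section 9.4.8 plans recruitment from Spring 2021 and adds "Provisions may be made depending on the novel coronavirus pandemic".

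Section 9.2 (sample size) is a heading without text.

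**The concern.** In a before-after comparison each teen is his or her own control. Gender, race/ethnicity, SES, age at entry and baseline BMI may show which teens changed more. They cannot bias the average change in the same teens, because they do not differ between the two visits. What can bias it is whatever moves between visits: growth, season, pandemic conditions, and the drift back expected after selection for high BMI. None of these is on the list.

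A report could therefore say that BMI was held or reduced after adjustment for confounders when the adjustment had not touched the estimate. Upward drift would hide a real benefit. Downward drift would credit a programme that did nothing.

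**Working it through.** The plan states no sample size, SD or effect, so there is no figure to reproduce. Steps 1 to 3 are algebra with a numerical check. Steps 4 to 6 rest on assumed inputs.

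**1. Fixed covariates drop out.** Let teen i have BMI y0 and y1 and a covariate x_i that is the same at both visits. Code visit as −½ and +½. The cross-product of visit and covariate is Σ x_i(−½ + ½) = 0. The two are orthogonal, so the visit coefficient equals mean(y1 − y0) whether or not x is in the model. The same holds with a random intercept. In a model of change on centred covariates, the intercept is again mean(y1 − y0).

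Numerical check, complete pairs:

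- Four simulated sets of 40 teens: the paired mean, least squares and mixed models with and without covariates, and the centred change model agreed to four decimals in each set (for example 0.4038 in all).
- Three simulated sets of 66 pairs, baseline BMI included: 0.1224, 0.0856 and 0.0873 in every version. Adding baseline BMI moved the standard error slightly in two sets (0.0991 to 0.0985; 0.0814 to 0.0785). The estimate did not move.

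**2. The time variable is the contrast.** With one fixed follow-up, time equals 0.25 year × post. The design [intercept, post, time] has rank 2 of 3. If visit intervals vary (0.20 to 0.35 year assumed), the two separate only by extrapolating to an interval of zero. The standard error is then about 0.98, against 0.15 for the paired change.

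**3. Age coded at each visit.** If baseline age is also in the model, age at visit is aliased (rank 3 of 4). Without baseline age, the estimate falls by the fitted age slope × 0.25 year. In simulation, 0.299 × 0.25 = 0.075, taking 0.264 to 0.189. That removes part of growth only.

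**4. Departures from the clean case.** With about 29% dropout related to age, the mixed-model estimate averaged 0.317 unadjusted and 0.321 adjusted, for a true drift of 0.3 and no effect. In logistic regression the post coefficient does change (0.12 to 0.87), because odds ratios are non-collapsible. The drift is not removed.

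**5. What drift could do.** Assume measurement SD 0.5 and between-teen slope SD 1.0 kg/m² per year. The SD of the 3-month change is √(2 × 0.5² + (0.25 × 1.0)²) = 0.75. Two sample sizes come from the earlier cohort in 2.2: 90 × 73% ≈ 66 (both arms) and 41 × 73% ≈ 30 (intervention arm). The standard errors are 0.75/√66 = 0.092 and 0.75/√30 = 0.137. A drift of 0.2, 0.5 or 1.0 per year shifts the change by 0.05, 0.125 or 0.25. The chance of declaring a rise with no effect is Φ(shift/SE − 1.96). The chance of detecting a true fall of 0.30 is Φ((0.30 − shift)/SE − 1.96).

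| Drift, kg/m² per year | False rise, n = 66 | False rise, n = 30 | Detect 0.30 fall, n = 66 | Detect 0.30 fall, n = 30 |
|---|---|---|---|---|
| 0.2 | 8% | 6% | 77% | 45% |
| 0.5 | 27% | 15% | 47% | 25% |
| 1.0 | 77% | 45% | 8% | 6% |

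By symmetry, downward drift of the same size gives false falls at the false-rise rates.

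**6. What does remove it.** Assume 40 teens, SD of change about 0.95, and no effect.

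| Drift over 3 months | Single arm, adjusted: mean change | Significant | Wait-list, adjusted: mean difference | Significant |
|---|---|---|---|---|
| 0 | 0.003 | 3.7% | −0.007 | 5.0% |
| 0.1 | 0.098 | 10.4% | 0.003 | 5.0% |
| 0.2 | 0.206 | 26.7% | −0.018 | 5.2% |
| 0.3 | 0.304 | 50.9% | −0.003 | 5.9% |

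The concurrent arm removes the drift. The covariates do not.

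**The case against.** **The design may be randomised.** Sections 4.1 and 5.5 describe a wait-list arm, and 9.4.1 refers to estimates for the intervention. In an arm comparison these covariates are ordinary and useful. This stands, and it limits the point to the before-after test that 9.4.1 writes, read with 6.3. A reader might infer that the covariate list is wrong in itself; the documents do not support that.

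**The outcome may be BMI percentile.** A percentile for age and sex absorbs average growth. This also stands. It leaves season, pandemic-period change and any regression to the mean. How large the last is depends on whether the chart BMI or the Visit 1 BMI qualifies the teen, which 5.1 does not say. The kg/m² figures above do not carry over to percentiles.

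**The list is open, and time is in the model.** A reader might infer that nothing in the model varies within a teen. That is too strong: time does, age might, and the list is given as examples. But time is the contrast itself, the coding of age is unstated, and no seasonal or calendar term is named.

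**A chart-based trajectory could rescue the test.** A reader might infer from 5.5 that a dated pre-programme BMI is already in hand. The query asks for "BMI (BMI percentile when available), medications prescribed, and laboratory values from the past year". It lists no date for BMI and no second value, and the one-year window reads as attached to the laboratory values. The scope of consent cannot be seen here, and community-referred teens may not be in the query.

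**Conclusion.** The point holds for the within-person before-after test in 9.4.1, taken with no randomisation. In linear or mixed models with complete pairs, the five listed covariates (age as age at entry) leave the mean change unchanged, so they do not adjust it for anything that moves between visits. This needs no assumed n or SD. It is not exact with dropout or in logistic regression, but in the checks run the drift remained there too.

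The documents do not fix the size or direction of any bias. The figures above illustrate assumed n, SD and drift. A reader might infer that the trial will report a false success; that would need downward drift, and nothing in the documents establishes it. If the wait list is run and the arm contrast is the test, shared drift cancels and the point falls away.

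**What to change.** Change 9.4.1 as follows, after reconciling 6.3 with 4.1 and 5.5:

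1. For any before-after contrast, delete the statement that the listed covariates adjust for confounding. Report the change as unadjusted for time-varying influences, and not as an intervention effect. Use the covariates, centred, only in covariate-by-time terms that describe who changed more.
2. If a wait-list arm is run, make the arm contrast at follow-up, adjusted for baseline, the test of effectiveness. Keep the present covariate list in that model.
3. Optionally, as a sensitivity analysis only, add a dated pre-baseline chart BMI where one exists and consent permits. State that it assumes a linear trajectory.

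Items 1 and 2 cost wording only. Item 3 needs a date recorded with each chart BMI and gives a wider interval. With a chart value 6 months before baseline, the change in trend over 3 months weights follow-up, baseline and chart BMI by 1, −1.5 and 0.5. Under the step 5 assumptions at n = 66, its standard error is 0.5 × √(1 + 2.25 + 0.25)/√66 = 0.115, about 25% above 0.092.
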